### **Study Design:**

In this proposed imaging correlative study, evaluation of muscle attenuation and mass will be determined using baseline CT scans collected for central review. A transverse cut at the L3 level will be extracted, as muscle area at this level is linearly related to whole body muscle mass. SliceOmatic software (version 5, Tomovision) will be used to process images, providing a highly accurate estimation of cross-sectional skeletal muscle area and muscle attenuation with high inter-observer reliability. The software is semi-automated and will be run by two independent investigators, with a subset of images read by both investigators to determine a coefficient of variation. LMM is defined as skeletal muscle index (SMI, lean muscle area/height, cm^2/m^2) less than 41 and LMA will be defined as average muscle density less than 25 HU, or less than 33 HU if the patient is overweight/obese by BMI. These cut-points are based on previously determined thresholds associated with reduced survival in patients with metastatic solid tumors. An additional exploratory objective will be to determine whether there are alternate cut-points predictive of survival in this particular population based on optimal stratification.

This evaluation will allow us to establish prevalence of LMM and LMA in this population, and to investigate the importance of muscle mass and quality, rather than body weight alone, on outcomes and toxicity in patients receiving AI-based therapy for MBC. This may lead to further refinement of prognostic/stratification criteria, support development of targeted exercise interventions, and investigation of AI drug resistance or alternate dosing strategies. In addition, the use of CT software to quickly calculate body composition measures may have important clinical applications across many treatments and disease types within ECOG-ACRN trials.

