#### Sample size and power justification:

We will plan initially to evaluate the study population as a whole (n=600), and later analyze the treatment and placebo groups separately (n=300 per group) once primary data are available. For the primary objective, assuming 60% of participants have LMA, we will have a 95% power to detect a difference in median survival time between 20 and 28 months (HR 1.4) for those with LMA versus those without LMA, based on a two- sided log rank test with type I error rate of 0.05. Reducing the sample size to 300 participants, we will achieve a 73% power to detect the same difference in median survival time.

Study population	% LMA	Median survival for LMA (month)	Median survival for non-LMA (month)	Hazard ratio	Study power(%)
600	60%	20	28	1.4	95
300	60%	20	28	1.4	73

Statistical analysis plan:

1. Primary aim:

- To determine the prognostic value of LMA on overall survival in patients receiving endocrine based therapy for metastatic breast cancer.
  - Kaplan Meier survival curve and log-rank test are used to test the difference in OS between the LMA participants and the non-LMA participants. Multivariable Cox proportional hazard model will be used to model the association between LMA and OS while adjusting for age, race, prior chemotherapy, ECOG PS and BMI.

2. Secondary aims:

- To determine the prognostic value of LMM on overall survival in patients receiving endocrine based therapy for metastatic breast cancer.
  - Kaplan Meier survival curve and log-rank test are used to test the difference in OS between the LMM participants and the non-LMM participants.
- To determine the prognostic value of LMA and LMM on overall survival in the subset of patients receiving endocrine based therapy for metastatic breast cancer who have sarcopenic obesity at study entry.
  - Kaplan Meier survival curve and log-rank test are used to test the difference in OS between the sarcopenic obese participants who had LMA or LMM and those without LMA or LMM.
- To assess correlation between LMA, LMM, and sarcopenic obesity with PRO\_CTCAE of muscle ache and joint pain at 3 months  
We will use two sample t-test to compare the muscle ache score or joint pain score between participants who had LMA (or LMM, or sarcopenic obesity) with those who didn't.
- To assess the correlation between LMA, LMM, and sarcopenic obesity with patient reported health related quality of life score at 3 months.  

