We will use two sample t-test to compare the quality of life score between participants who had LMA (or LMM, or sarcopenic obesity) with those who didn't.
- To determine the optimal stratification for LMA and LMM to predict overall survival.
  - We will use a search algorithm, together with the method of the time-dependent ROC curve to determine the optimal cut-off point for the determination of LMA and LMM to identify groups with differential overall survival.

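### Appendix X sets out to study muscle rather than body weight, but outside the LMA survival model its low-muscle-mass survival test and month-3 score comparisons do not separate the two

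*Combined protocol and SAP*

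**What the plan says.** The Background of Appendix X argues that weight-based measures such as BMI have given inconsistent results. Under Study Design, the evaluation is meant to "investigate the importance of muscle mass and quality, rather than body weight alone, on outcomes and toxicity".

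The Statistical analysis plan of the same appendix then treats the aims differently:

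- **LMA and OS (primary aim).** A log-rank test plus a multivariable Cox model to "model the association between LMA and OS while adjusting for age, race, prior chemotherapy, ECOG PS and BMI".
- **LMM and OS (secondary aim).** "Kaplan Meier survival curve and log-rank test are used to test the difference in OS between the LMM participants and the non-LMM participants". No model, covariate or stratification follows.
- **Survival in sarcopenic obesity (secondary aim).** A log-rank test of "the difference in OS between the sarcopenic obese participants who had LMA or LMM and those without LMA or LMM".
- **Month-3 muscle ache, joint pain and quality of life (secondary aims).** Two-sample t-tests of "participants who had LMA (or LMM, or sarcopenic obesity) with those who" did not. No covariates are named.

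The definitions differ as well. LMA has a BMI-dependent threshold (25 HU, or 33 HU if overweight or obese). LMM has one threshold, a skeletal muscle index (SMI) below 41, for every patient. Sarcopenic obesity is not defined anywhere in the documents.

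**The concern.** If SMI rises with BMI, a single cut-off places thinner patients in the LMM group more often than heavier ones. If BMI also bears on survival, the crude LMM contrast carries that effect. Section 9.4 of the main protocol names BMI among known prognostic factors for its PFS and OS models, and the LMA model adjusts for it. The plan's authors thus regarded BMI as relevant, and they give no reason for leaving it out for LMM.

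The month-3 sarcopenic-obesity contrast has a different fault. Its comparator pools non-obese patients with obese patients who have adequate muscle, so a difference may reflect obesity, muscle or both, and the test cannot say which. The LMA and LMM t-tests in the same sentences are equally unadjusted.

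At stake is how these secondary results are read. The appendix foresees use in prognostic or stratification criteria and in targeted exercise interventions. Those uses depend on muscle mattering beyond weight.

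**Working it through.** **The plan's own figures.** The appendix states power only for LMA: 95% with 600 patients and 73% with 300 (60% LMA, HR 1.4, two-sided 0.05). By Schoenfeld's formula these need 479 and 244 deaths, about 80% of patients in each case, so they agree with each other. They do not bear on this point. The plan gives no figure for LMM or for the month-3 tests.

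**Inputs from the documents.** 600 patients; 410 deaths at the final OS analysis (Section 9.2.2); two-sided alpha 0.05 (Appendix X); about 324 patients analysable for quality of life at month 3, from the first 360 enrolled (Sections 9.6 and 9.6.1). I apply 324 to the PRO-CTCAE muscle and joint items too, which is an assumption.

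**Inputs not in the documents (assumed).** No true muscle effect; 50% LMM; SMI-BMI correlation r of 0.4 to 0.6; BMI hazard ratio of 0.80 to 0.90 per SD. For the t-tests: 40% obese, half of those sarcopenic, and an obesity effect of 0.2 to 0.4 SD on the score.

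**LMM log-rank.** With SMI split at its median, mean BMI differs between the groups by 1.596 × r SD (1.596 = 2 × 0.798, for a normal variable split at its median). The crude log hazard ratio is then about 1.596 × r × |ln(BMI HR)|, and z = log HR × √(410 × 0.25) = log HR × 10.12. The rejection probability is approximately P(Z > 1.96 − z) + P(Z < −1.96 − z).

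- r = 0.4, BMI HR 0.90: 0.638 × 0.1054 = 0.067; HR 1.07; z = 0.68; rejection 10.5%. Simulation (2,000 trials per setting, 40 months of accrual, cut at month 64): 10.6%.
- r = 0.6, BMI HR 0.80: 0.958 × 0.2231 = 0.214; HR 1.24; z = 2.16; rejection 58%. Simulation: 55.0%, HR 1.23.
- BMI HR 1.0: rejection 5%. Simulation: 4.5% to 5.4%.

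**Direction.** A second calculation uses a binary high-BMI factor, again with no muscle effect, 50% LMM and 410 deaths:

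| High BMI, LMM vs non-LMM | BMI HR 0.9 | BMI HR 0.75 | BMI HR 0.6 | BMI HR 1.3 |
|---|---|---|---|---|
| 45% vs 65% | 1.02 (5%) | 1.06 (8%) | 1.10 (17%) | 0.95 (9%) |
| 35% vs 75% | 1.04 (7%) | 1.12 (20%) | 1.22 (53%) | 0.90 (19%) |
| 25% vs 85% | 1.06 (9%) | 1.19 (40%) | 1.35 (87%) | 0.85 (37%) |

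Cells show the crude LMM hazard ratio and, in brackets, the rejection probability. If high BMI is protective, LMM looks harmful. If high BMI is harmful, LMM looks protective, and a real muscle effect could be hidden. The last row supposes a very strong link between BMI and LMM.

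**Month-3 sarcopenic-obesity t-test.** Sarcopenic-obese patients make up 0.40 × 0.5 = 20%. Among the other 80%, the obese share is 20/80 = 25%. The spurious difference is therefore shift × (1 − 0.25), or 0.15 to 0.30 SD. With 324 patients the groups are 64.8 and 259.2, and the standard error is √(1/64.8 + 1/259.2) = 0.139 SD.

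- Shift 0.2: z = 0.15/0.139 = 1.08; rejection 19%.
- Shift 0.3: z = 0.225/0.139 = 1.62; rejection 37%.
- Shift 0.4: z = 0.30/0.139 = 2.16; rejection 58%.

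**The case against.** The secondary hypothesis says only that LMM is prognostic of poor survival. That is a marginal claim, and a log-rank test answers it. The phrase about body weight can be read as contrasting two metrics, without promising independence from BMI in every secondary aim. Sarcopenic obesity is a composite by construction, so measuring obesity and muscle together is arguably what its objective asks. Muscle is also part of body mass, so adjusting for BMI may remove real signal.

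Much of this stands. The log-rank is a valid test of its literal hypothesis and should stay. It does not meet the purpose given under Study Design, and one extra model does.

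Three stronger readings are tempting and are not supported:

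- *All the sarcopenic-obesity comparisons ignore body weight.* The survival comparison is run inside the sarcopenic-obese subset, so it controls obesity coarsely by restriction. Its difficulties lie elsewhere: the missing definition and, if sarcopenic means low muscle mass, a nearly empty group without LMM.
- *A weight effect will be reported as a muscle effect.* That needs BMI to be related to both LMM and the outcome. The documents quantify neither link, and the appendix itself calls the BMI literature inconsistent.
- *The substudy never tests muscle beyond weight.* The primary LMA aim does so, with BMI in its Cox model.

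**Conclusion.** The concern holds for two parts of Appendix X: the LMM survival test and the month-3 score comparisons. In both, a body-weight effect could appear as, or conceal, a muscle effect.

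Under the per-SD assumptions the LMM false-positive rate is about 5% if BMI is unrelated to survival, rising to about 55% at a correlation of 0.6 and a BMI hazard ratio of 0.80 per SD. The binary-BMI scenarios span 5% to 87%, with the sign reversing if high BMI is harmful. For the sarcopenic-obesity t-tests the rate is about 19% to 58%. These figures illustrate sensitivity and do not predict the trial, because no BMI association can be taken from the documents.

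Severity is minor. These are secondary aims of a correlative substudy, without stated power, and they leave the PFS and OS conclusions untouched.

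**What to change.** In the Statistical analysis plan of Appendix X:

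1. **LMM and OS.** Report the Cox model already specified for LMA (age, race, prior chemotherapy, ECOG PS, BMI) alongside the log-rank test. Base any claim about muscle beyond weight on the adjusted estimate.
2. **Month-3 scores.** Adjust the LMA and LMM comparisons for BMI, for example by linear regression. Define sarcopenic obesity. Compare sarcopenic-obese patients with obese patients who are not sarcopenic, and show non-obese patients as a separate group.

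The cost is a few lines of text and a little programming. Height, weight and ECOG PS are collected at baseline (Section 7), and the remaining covariates are already required for the LMA model. The price is slightly wider intervals and a smaller comparator for sarcopenic obesity. BMI may absorb some muscle signal, so the crude results should still be shown beside the adjusted ones.

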- \_\_\_\_\_ 3.1.5 Sexually active males and pre/perimenopausal women must agree to use an accepted and effective method of contraception or to abstain from sexual intercourse for the duration of their participation in the study and for 3 months after discontinuation of therapy.

Rev.10/15

- \_\_\_\_\_ 3.1.6 Women must not be pregnant or breast-feeding.
- All females of childbearing potential must have a blood test or urine study  $\leq$  2 weeks prior to randomization.
- A female of childbearing potential is any woman, regardless of sexual orientation or whether they have undergone tubal ligation, who meets the following criteria: 1) has not undergone a hysterectomy or bilateral oophorectomy; or 2) has not been naturally postmenopausal for at least 24 consecutive months (i.e., has had menses at any time in the preceding 24 consecutive months).

Female? \_\_\_\_\_ (Yes or No)

Date of blood test or urine study: \_\_\_\_\_

- \_\_\_\_\_ 3.1.7 Patients must not have known central nervous system metastasis or a history of CNS metastases. Patients with leptomeningeal disease are not eligible.

- \_\_\_\_\_ 3.1.8 Patients must be disease-free of prior invasive malignancies for  $>$  5 years with the exception of curatively-treated basal cell or squamous cell carcinoma of the skin or carcinoma in situ of the cervix.

**NOTE:** If there is a history of prior malignancy, patients must not be receiving other specific treatment for that cancer.

Rev. 4/15

- \_\_\_\_\_ 3.1.9 Patients must meet at least one of the following criteria:
- \_\_\_\_\_ 3.1.9.1 Disease progression any time after non-steroidal AI use in the advanced disease setting.

Rev. 10/15  
Rev. 10/16

3.1.9.2 Relapse while on or within  $\leq 12$  months of end of adjuvant non-steroidal AI therapy with or without prior endocrine therapy for advanced disease.

**NOTE:** In either setting, treatment with any prior endocrine therapy must be completed  $\geq 2$  weeks prior to C1D1 of study treatment with the exception of exemestane which is permitted in the advanced disease setting within  $\leq 4$  weeks immediately prior to C1D1. Prior adjuvant exemestane is allowed if the disease free interval is  $>12$  months from the discontinuation of exemestane. Prior faslodex, everolimus, palbociclib or other CDK inhibitor (e.g. ribociclib, abemaciclib) use are allowed and must have been completed  $\geq 2$  weeks prior to C1D1. Failure to adhere to this washout guideline will result in a protocol violation.

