- 1) Baseline (before Cycle 1 Day 1)
  - 2) End of Cycle 3
  - 3) End of Cycle 6
  - 4) End of Cycle 12
  - 5) At end of protocol treatment, including treatment discontinuation for any reason (i.e. toxicity, progression, completion of protocol therapy)
- Rev. Add5 5.6.3.5 PRO-CTCAE: PRO-CTCAE items will be administered
- 1) Baseline and prior to every cycle, following the same schedule as trial symptom/toxicity assessments.
  - 2) End of each Cycle during treatment
-

- 3) At end of protocol treatment, including treatment discontinuation for any reason (i.e. toxicity, progression, completion of protocol therapy)

**NOTE:** The PRO-CTCAE should be completed each time a Symptom/Toxicity Assessments is completed.

The total length of this assessment is dependent on the assessment time point. One of the lengthiest assessments will occur at Baseline (FACT-G, PROMIS-fatigue, FAACT-subscale, FACIT-diarrhea subscale, FBSI, PRO-CTCAE) is 80 multiple choice items. The anticipated time to complete all items is roughly 15-20 minutes. Assessments prior to cycles 4, 7 and 13 will also include the ECOG-ACRIN Medication Adherence Scale Modified from the Morisky Index that will include 8 multiple choice or yes/no items and will take roughly 2-3 minutes. This assessment schedule corresponds to the first, second, and fourth disease assessments. We have scheduled PRO assessments with standard clinic office visits to minimize participant and site burden, thus minimizing the risk of missing PRO data. Assessments to be administered at every cycle (FBSI, PRO-CTCAE) will include 21 multiple choice items and will take 4-5 minutes to complete.

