**Background**

Observational data investigating the relationship between body habitus and outcome or toxicity in breast cancer has been largely centered on weight-based metrics such as BMI, with variable and inconsistent results. Body weight alone does not tell a full story, as body composition is highly variable with respect to muscle and adipose tissue. Muscle is a large, active endocrine organ affecting physical function, quality of life, metabolism, and inflammation, and may impact outcome or toxicity in metastatic breast cancer (MBC) patients receiving endocrine based therapies.

Rev. Add7

Low muscle mass (LMM) has been associated with poorer outcome and increased toxicity in advanced cancer. Low muscle attenuation (LMA), reflecting muscle “quality” and intramuscular fat infiltration, is also associated with poor outcome. In comparison to muscle mass, muscle attenuation correlates better with muscle strength and function. The few studies that have investigated these parameters in patients with MBC have been small and focused on patients receiving cytotoxic chemotherapy. The largest of these was a retrospective study of patients receiving first line chemotherapy, finding no significant difference in overall survival based on LMM (40 versus 30 months,  $p=0.07$ ), but a significantly reduced survival for those patients with LMA (23 versus 15 months,  $p = 0.005$ ).

To date, there has been no evaluation of how muscle characteristics affect outcome or toxicity in patients receiving endocrine therapy for MBC. The ongoing study E2112, a randomized, double-blinded phase III study of exemestane with or without the HDAC inhibitor entinostat with co-primary objectives of progression free survival (PFS) and/or overall survival (OS), offers a homogeneous population with centrally collected imaging and outcome follow-up to investigate this question.

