**Objectives:**

1. Primary: To determine the prognostic value of baseline LMA by CT imaging on overall survival in patients receiving endocrine based therapy for MBC.
2. Secondary:
  - To determine the prognostic value of baseline LMM by CT imaging on overall survival in patients receiving endocrine based therapy for MBC.

- To determine the prognostic value of LMA and LMM on overall survival in the subset of patients receiving endocrine based therapy for metastatic breast cancer who have sarcopenic obesity at study entry.
- To assess the correlation between LMA, LMM, and sarcopenic obesity with PRO\_CTCAE of muscle ache and joint pain at 3 months.
- To assess the correlation between LMA, LMM, and sarcopenic obesity with patient reported health related quality of life score at 3 months.
- To determine the optimal stratification for LMA and LMM to predict overall survival.

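### Appendix X: unadjusted month-3 comparisons by muscle group cannot separate symptoms present before Cycle 1 from those arising on study treatment

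*Combined protocol and SAP*

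**What the plan says.** The Background of Appendix X gives the gap to be filled: "To date, there has been no evaluation of how muscle characteristics affect outcome or toxicity in patients receiving endocrine therapy for MBC". Its Study Design text repeats the purpose, to study the importance of muscle mass and quality "on outcomes and toxicity in patients receiving AI-based therapy for MBC".

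The matching secondary objectives are narrower. They ask for the correlation of low muscle attenuation (LMA), low muscle mass (LMM) and sarcopenic obesity with patient-reported scores "of muscle ache and joint pain at 3 months", and likewise with the quality-of-life score at 3 months.

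The analysis text for aches is "We will use two sample t-test to compare the muscle ache score or joint pain score between participants who had LMA", set against those without it; the same test is planned for LMM and for sarcopenic obesity. For quality of life it is "We will use two sample t-test to compare the quality of life score between participants who had LMA", with the same alternatives. Neither names a baseline score, a change score or a covariate. Within Appendix X, covariates appear only in the Cox model for overall survival (OS): age, race, prior chemotherapy, ECOG PS and BMI.

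Baseline scores exist. Section 5.6.3.5 schedules PRO-CTCAE at "Baseline and prior to every cycle, following the same schedule as trial symptom/toxicity assessments". Section 5.6.3.4 and footnote 7 of the Section 7 calendar schedule FACT-G before Cycle 1 Day 1 and at the end of Cycle 3.

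**The concern.** Muscle status is read from the baseline CT, so the groups may differ in age, performance status, disease burden and symptoms before study drug. The documents give two reasons to expect this:

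- Appendix X says that muscle affects physical function and quality of life, and that attenuation tracks strength and function. The HRQL score in Section 9.6.1 is built from FACT-G physical and functional items.
- Every patient has had a non-steroidal AI. Section 3.1.9 requires either "Disease progression any time after non-steroidal AI use in the advanced disease setting" or relapse on, or within 12 months of, adjuvant treatment. Its note also permits exemestane in the advanced setting shortly before Cycle 1. Aches at entry are therefore plausible.

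If such a difference exists and persists unchanged, the month-3 test will tend to be significant even when symptoms change by the same amount in both groups. Read against the stated toxicity purpose, that result could be taken as a sign that low muscle makes study treatment harder to tolerate.

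**Working it through.** **Inputs from the documents**

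- Share with LMA: 60% (Appendix X, sample size).
- Month-3 sample: Section 9.6 limits PRO evaluation to treated patients among the first 360. Section 9.6.1 expects 10% attrition: 360 × 0.90 = 324. At 60/40 this is 194 versus 130.
- HRQL standard deviation 12 points; 5 points is called clinically meaningful (Section 9.6.1).

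**Assumptions**

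- Two-sided 5% level. Appendix X states it for the OS test and gives none for these t-tests.
- Baseline gap by muscle group: not given; taken as 0, 0.1, 0.2 or 0.3 SD.
- Same mean change from baseline in both groups, and normal scores with equal variance.

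**The plan's nearest figure.** Appendix X gives no power for these comparisons. The closest is the between-arm HRQL test in Section 9.6.1: 162 per arm, difference 5, SD 12, two-sided 0.025.

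SE = 12 × √(2/162) = 1.333; 5/1.333 = 3.75; power = Φ(3.75 − 2.241) = 93.4%. The plan says about 93%, so it reproduces.

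**Month-3 test by muscle group.** With equal change, the expected month-3 difference equals the baseline gap d.

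SE in SD units = √(1/194 + 1/130) = 0.1133. The chance of significance is approximately Φ(d/0.1133 − 1.96) + Φ(−d/0.1133 − 1.96).

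| Assumed gap (SD) | On the HRQL scale (SD 12) | d/SE | Chance that the month-3 test is significant |
|---|---|---|---|
| 0 | 0 points | 0 | 5% |
| 0.1 | 1.2 points | 0.88 | 14% |
| 0.2 | 2.4 points | 1.76 | 42% |
| 0.3 | 3.6 points | 2.65 | 75% |

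Simulation (3,000 runs per setting) agrees. All three gaps lie below the 5 points that the protocol treats as meaningful.

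**Two ways of using the baseline score.** In the same simulations the t-test on change from baseline was significant in about 4 to 5% of runs at every gap examined. A model of the month-3 score adjusted for baseline behaves differently, because it leaves (1 − correlation) × gap. At a 0.3 SD gap and baseline-to-month-3 correlations of 0.3, 0.5 and 0.7 (assumed), it leaves 0.21, 0.15 and 0.09 SD and is significant in 50%, 34% and 20% of runs. With non-randomized groups the two analyses answer different questions, so the plan must name the one it wants.

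**Practice elsewhere in the protocol.** Section 9.7.2 relates HRQL after treatment to adherence groups, which are also non-randomized, and adjusts for baseline HRQL and patient characteristics. Section 9.6.2 compares change from baseline to month 3 between the randomized arms. Appendix X does neither.

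**The case against.** The strongest reply is that the objective asks for a correlation at 3 months, and for that question a two-sample test of month-3 scores is valid. This stands. A reader might infer that the plan counts pre-existing symptoms as a treatment effect. The documents do not say so: toxicity appears in the Background and Study Design text, and the quality-of-life objective is never called toxicity.

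A reader might also take 14% to 75% as inflated type I error. It is not. The test's null is equal month-3 scores, which is false whenever the assumed gap persists, so these are powers against a real month-3 difference. What they show is that a significant result says little about on-study change. The pattern follows from the assumptions, and with no gap the test holds 5%.

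Third, replacing the month-3 comparison with a change score could discard part of what the substudy seeks. Aches at entry may already come from an earlier AI, and the stated question is not limited to symptoms that begin after Cycle 1. This also stands, and it is why the change analysis should be added and not substituted.

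Finally, Appendix X says only that the evaluation as a whole, with OS as its primary endpoint, may lead to work on exercise or dosing. A reader might infer that these t-tests would drive such decisions; the text does not support that.

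**Conclusion.** The point holds as a limit on interpretation. The month-3 tests meet the cross-sectional objective but cannot inform the toxicity purpose, because they do not separate differences present before Cycle 1 from differences arising on study treatment. A pre-existing gap of 0.1, 0.2 or 0.3 SD would give a significant result in about 14%, 42% or 75% of analyses with no differential change.

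Those figures rest on assumed gaps, equal change in both groups and about 324 patients. Larger percentages follow if 540 patients are assumed (600 less 10%), but Section 9.6 excludes the last 240 patients from PRO evaluation, so that basis is not supported. Whether any baseline gap exists is unknown until baseline scores are tabulated by muscle group. The aims are secondary and sit in a substudy, no trial endpoint depends on them, and the importance is low.

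**What to change.** In the Appendix X analysis plan, for muscle ache, joint pain and HRQL:

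1. Keep the month-3 comparison, label it cross-sectional, and state that it is not evidence of on-study toxicity.
2. Report baseline scores by muscle group beside it.
3. Add a comparison of change from baseline to month 3 by muscle group, adjusted for treatment arm and the covariates already named for the OS Cox model (age, race, prior chemotherapy, ECOG PS, BMI).
4. State that baseline aches may already reflect prior AI therapy, so the change analysis addresses on-study change only, and that residual confounding remains.

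The cost is appendix wording and some analysis work; no new visit, form or patient is needed. Patients without a baseline form drop out of the added analysis. Adjustment for arm needs unblinded data, so it belongs with the by-arm analyses that Appendix X already defers until the primary data are available.

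### Appendix X searches the trial data for the LMA and LMM cut-offs that best separate overall survival and plans no internal validation or correction, so the separation shown at the chosen cut will be optimistic

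*Combined protocol and SAP*

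**What the plan says.** Appendix X uses muscle cut-offs in two ways.

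- **Fixed cut-offs.** Study Design defines LMM as a skeletal muscle index below 41, and LMA as average density below 25 HU (below 33 HU if overweight or obese). It explains that "These cut-points are based on previously determined thresholds associated with reduced survival in patients with metastatic solid tumors". The primary LMA comparison and the secondary LMM comparison are Kaplan–Meier and log-rank analyses of groups so defined. The power statement concerns the fixed LMA definition: "assuming 60% of participants have LMA, we will have a 95% power" at n=600, "based on a two- sided log rank test with type I error rate of 0.05".
- **Searched cut-offs.** The last secondary aim in the statistical analysis plan reads "We will use a search algorithm, together with the method of the time-dependent ROC curve to determine the optimal cut-off point", and the sentence continues "for the determination of LMA and LMM to identify groups with differential overall survival". It gives no search range, ROC time point, hold-out set, cross-validation, bootstrap or adjusted P-value. It also names no test at the searched cut.

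The status of the search differs between sections. Objectives lists it as secondary: "To determine the optimal stratification for LMA and LMM to predict overall survival". Study Design calls it exploratory: "An additional exploratory objective will be to determine whether there are alternate cut-points predictive of survival in this particular population based on optimal stratification".

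**The concern.** A cut chosen because it separates survival well in one set of patients will separate those patients better than it separates new ones. The hazard ratio read off at that cut is biased away from 1. A P-value computed as if the cut had been fixed beforehand does not hold its nominal level. The aim is to produce groups that differ in survival, and the trial patients are the only ones in whom the plan provides for describing them.

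At stake is whether a new LMA or LMM threshold reported from this substudy can be believed. An uncorrected threshold could be carried into later work with an overstated effect and then fail to replicate.

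**Working it through.** **1. The plan's own figures.** Appendix X states no error rate for the search. It states only power at the fixed LMA cut: 95% (n=600) and 73% (n=300), for medians of 20 and 28 months (HR 1.4) and 60% LMA.

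Take exponential survival, uniform accrual over 40 months and analysis at 70 months (timing from Section 9.2.2). The proportion who die in a group with hazard λ = ln 2/median is 1 − [e^(−30λ) − e^(−70λ)]/(40λ):

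- median 20 months: 0.809
- median 28 months: 0.698
- mixture: 0.6×0.809 + 0.4×0.698 = 0.764, so about 459 deaths of 600, or 229 of 300

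Freedman's formula for unequal groups is power = Φ(√(dk)·|1−HR|/(1+k·HR) − 1.96). With k = 2/3:

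- d = 458.7: 17.49×0.4/1.933 = 3.618, and Φ(1.658) = 95.1%
- d = 229.3: 12.36×0.4/1.933 = 2.558, and Φ(0.598) = 72.5%

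Both stated figures are reproduced in that orientation of the formula. With k = 1.5 it gives 92.3% and 66.8%, and Schoenfeld's formula gives 94.2% and 70.4%. These figures concern the fixed cut and say nothing about the search.

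**2. Analytic check of a log-rank-maximising search.** For a search between quantiles ε and 1−ε, the Miller–Siegmund approximation under no association is

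P(max|Z| > z) ≈ 4φ(z)/z + φ(z)(z − 1/z)·ln[(1−ε)²/ε²].

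At z = 1.96, φ = 0.0584, the first term is 0.119 and φ(z − 1/z) = 0.0847.

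- Central 50% (ε = 0.25): 0.119 + 0.0847×ln 9 = 0.119 + 0.186 = 30.5%
- Central 80% (ε = 0.10): 0.119 + 0.0847×ln 81 = 0.119 + 0.372 = 49.2%

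**3. Simulation with no true association.** Inputs: exponential survival with median 24 months, 40 months of accrual and 24 of follow-up, giving about 422 deaths at n=600 and 211 at n=300 (Section 9.2.2 plans 410 for the main trial). The cut is chosen by each method, then tested by an ordinary two-sided 5% log-rank test in the same patients. Ranges cover both sample sizes and repeat runs.

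| Choice of cut | Nominally significant |
|---|---|
| Fixed in advance (60% point) | 4.8–4.9% |
| Youden point, ROC at 12 months | 17–21% |
| Youden point, ROC at 24 months | 22–32% |
| Maximal log-rank, central 50% | 30–32% |
| Maximal log-rank, central 80% | 45–48% |

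The 32% for the Youden search came with no limit on the range; within the central 80% the highest value was 31%. The fixed-cut row shows that the inflation comes from the search.

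**4. Apparent effect at n=600, truth 1.0.** The median hazard ratio at the chosen cut is about 1.12–1.18 with the Youden search, and 1.18 (central 50%) to 1.25 (central 80%) with the log-rank search.

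**5. Two markers.** If LMA and LMM were independent (an assumption), 17% per marker becomes 1 − 0.83² = 31% for at least one false positive, and 48% becomes 1 − 0.52² = 73%.

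**6. Threshold needed.** Holding a log-rank-maximising search at 5% needs |Z| above about 2.83 (nominal P 0.0047) for the central 50%, or 3.05 (P 0.0023) for the central 80%, in place of 1.96.

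**The case against.** The strongest reply is that the plan never says it will test the searched cut. Where Appendix X tests survival it names the log-rank test, and for the search it names only an algorithm and a time-dependent ROC curve. Study Design labels the search exploratory. The confirmatory comparisons rest on external thresholds. Any false-positive rate therefore belongs to a test and a search range that a reader has supplied.

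Most of this stands. A reader might infer that, under the plan as written, a worthless marker would look prognostic in a third to a half of analyses. The documents do not support that. Those rates need a log-rank-maximising search, a chosen range and an uncorrected test, and the ROC method that is named gives lower figures. The unspecified search algorithm does not exclude log-rank maximisation, so the higher figures remain possible.

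A reader might also infer that the substudy's main prognostic results are compromised, or that the searched cut-offs will be adopted. Neither follows. The main tests use fixed cut-offs. The remark in Study Design about refining prognostic criteria concerns the substudy as a whole and is only tentative.

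What the reply does not remove is the optimism in the estimate. It arises whether or not a P-value is printed, and an exploratory label does not correct it. The label is also contradicted by the Objectives and by the analysis plan, which place the search among the secondary aims.

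**Conclusion.** The concern holds for the cut-off search alone and is minor for the trial. Following Appendix X as written yields an optimistic survival separation at the searched LMA and LMM cut-offs, because selection and description use the same patients and nothing corrects for it.

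The sizes are conditional. Assuming a search over the central 50–80% of the marker and an ordinary 5% log-rank test at the chosen cut, the nominal false-positive rate per marker is about 17–32% for the ROC approach the plan names (Youden point, 12–24 months) and about 30–48% if the algorithm maximises the log-rank statistic. The median apparent hazard ratio is about 1.12–1.25 under no effect at n=600. Even the lowest rate is more than three times the nominal 5%.

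**What to change.** - For any cut-off reported from the search, give a bootstrap optimism-corrected hazard ratio, repeating the whole search in each resample.
- If a P-value is given at that cut, adjust it for the search, by a maximally selected rank statistic or by permutation.
- State the search range, the search criterion and the ROC time point before the analysis.
- Show LMA and LMM alongside as continuous terms (splines) in the Cox model. This does not replace the search for a stratification, but it shows whether a threshold is a sensible summary.
- Call the aim either secondary or exploratory, and use the same term in Objectives, Study Design and the analysis plan.

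No new data are needed. The cost is a few lines of text, a small amount of computing and a reported effect that will look less striking.
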